### 5.9.6.2 Pharmacokinetic Analyses

$C_{max}$  and AUC are the primary PK parameters of interest in PK similarity studies with extravascular drug administration. These and additional PK parameters (i.e.,  $t_{max}$ , half-life, elimination rate) will be determined for each subject using non-compartmental methods. All parameters will be reported with standard descriptive statistics including the geometric mean and coefficient of variation. Calculation of PK parameters will be performed using actual sampling times.

## 5.9.7 Additional Analyses

### 5.9.7.1 Proteomics and small RNA Transcriptomics Analysis

A combination of differential expression testing of signals analysis, and clustering techniques will be used demonstrate subject response to each product. Differentially expressed plasma proteins and small RNAs will be identified using a 10% false discovery rate. Following technical and independent validation of the most promising or top 1% biomarker(s), dose- and exposure-response analysis will be performed as described above for the primary biomarker(s). The AUEC change along with maximal effect at a single

time point for a promising biomarker(s) will also be calculated. The values, variability and characteristics of the proteomic-array-based biomarker will be compared to the traditional biomarker analysis outlined above. Based on proteomic and small RNA transcriptomic findings, the potential for a composite of relevant biomarkers to demonstrate PD similarity will also be evaluated. Additional details regarding the statistical methods for the proteomic and small RNA transcriptomic analyses will be described in a separate protocol.

#### **5.9.7.2 Genomic Analysis**

Genetic variation may contribute to the PK or PD response to a drug. Analyses of buffy coat DNA may include genome-wide studies, including (but not limited to) the generation of variant data and/or genomic sequencing in hypothesis-generating studies. Additional details regarding the statistical methods for the genomic analyses will be described in a separate protocol.

#### **5.9.7.3 Other Omic Analyses**

Epigenetic variation such as DNA methylation has the capacity to contribute to the PD or PK response to a drug. Moreover, profiling metabolites in biofluids may have utility in the identification of circulating PD biomarkers. The generation of additional omics profiles (e.g., metabolomics and methylomics) from an alternative biospecimen such as urine can inform on the utility of these technologies for PD biomarker identification and the analytical framework required for future studies involving this biospecimen. These analyses may also inform on biofluid specificity. These analyses will be considered hypothesis-generating. Additional details regarding the statistical methods for the omics analyses will be described in a separate protocol.

### **5.9.8 Safety Analyses**

#### **5.9.8.1 Adverse Events**

All AEs will be coded using the latest version of the Medical Dictionary for Regulatory Activities. The incidence of TEAEs, organized by system organ class and frequency, will be summarized by seriousness, severity, relationship to treatment, and by treatment at onset of the TEAE. A detailed listing of serious AEs and TEAEs leading to withdrawal will also be provided.

#### **5.9.8.2 Clinical Laboratory Tests**

Clinical laboratory results (hematology, serum chemistry, and urinalysis) will be summarized using descriptive statistics (number of subjects, mean, SD, minimum, median, and maximum). Clinical laboratory results will be classified as normal or abnormal, according to the reference ranges of the individual parameter. The number and

percentage of subjects with abnormal laboratory results will be provided. No statistical testing will be performed on clinical laboratory data.

### **5.9.8.3 Vital Sign Measurements**

Vital sign measurements and changes from baseline will be summarized using descriptive statistics (number of subjects, mean, SD, minimum, median, and maximum) by treatment and time point.

### **5.9.8.4 Safety 12-lead Electrocardiograms**

Safety 12-lead ECG data and changes from Baseline will be summarized using descriptive statistics (number of subjects, mean, SD, minimum, median, and maximum) by treatment and time point. The extent of change in each of the treatments will also be compared. The incidence of pathological ECG interpretive statements at Baseline and during treatment will be assessed among the treatments.

### **5.9.8.5 Physical Examinations**

Physical examination findings will be presented in a data listing, and abnormal physical examination findings will be recorded as AEs.

### **5.9.8.6 Other Safety Data**

All concomitant medication usage and medications that changed in daily dose, frequency, or both since the subject provided informed consent will be summarized for each subject.

### **5.9.9 Interim Analyses**

No interim analyses are planned.

### **5.9.10 Missing Data**

Missing data will not be imputed. Data that are excluded from the descriptive or inferential analyses will be included in the subject data listings. This will include data from subjects not in the particular analysis population, measurements from unscheduled visits, or extra measurements that may arise from 2 or more analyses of a plasma sample at the same time point.

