### **Safety**

The safety population will include all subjects who receive at least 1 dose of any of the study drugs. Any AEs will be coded using the Medical Dictionary for Regulatory Activities (MedDRA). The incidence of AEs, organized by system organ class and preferred term, will be summarized with a focus on treatment-emergent AEs. Vital sign measurements will be summarized using descriptive statistics by time point. All values will be evaluated for clinically notable results. Data for additional safety parameters (e.g., physical examination findings) will be listed.

**Date of Protocol:** 17 August 2020

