**Table 5-2: Clinical Laboratory Tests and Diagnostic Screening Tests**

Hematology	Serum Chemistry	Urinalysis	Lipid Panel
Hematocrit Hemoglobin Platelet count Red blood cell count White blood cell count (with automated differential)	Alanine aminotransferase Albumin Alkaline phosphatase Aspartate aminotransferase Bicarbonate Bilirubin (total, direct, and indirect) Blood urea nitrogen Calcium Chloride Creatinine (including calculated creatinine clearance) Glucose Lactate dehydrogenase Magnesium Phosphorus Potassium Sodium Total protein Uric acid	Appearance Bilirubin Blood Color Glucose Ketones Leukocyte esterase Microscopic examination: red blood cells, white blood cells, epithelial cells, bacteria, crystals, and casts (if present) Nitrite pH Protein Specific gravity Urobilinogen	Total cholesterol High-density lipoprotein cholesterol (HDL-C) Low-density lipoprotein cholesterol (LDL-C) Triglycerides
Diagnostic Screening Tests:			
Serum	Urine	Other	
Serology (human immunodeficiency virus Ag/Ab Combo 1/2, hepatitis C virus antibody, and hepatitis B surface antigen) Female Subjects Only Human chorionic gonadotropin (for pregnancy)	Drug screen including: amphetamines, barbiturates, benzodiazepines, cannabinoids, cocaine, alcohol, opiates, phencyclidine, propoxyphene, and methadone	SARS-CoV2 molecular test	

Clinical laboratory results will be reviewed by the investigator or designee together with data in the eCRF. Any values outside the reference range will be evaluated for clinical significance. If a value is determined to be clinically significant, the subject will be instructed to follow-up with his or her personal physician. The investigator or designee may repeat the clinical laboratory tests if deemed appropriate. The investigator will maintain a copy of the laboratory accreditation and the reference ranges for the laboratory used.

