#### **7.7.4 Safety 12-lead Electrocardiograms**

The incidence of pathological ECG interpretive statements at Baseline and during treatment will be assessed among the treatments.

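### Protocol 5.9.10 leaves unscheduled-visit measurements out of descriptive analyses with no exception for safety data, and the SAP does not say whether they count towards laboratory and ECG abnormality summaries

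*Protocol*

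**What the plan says.** Protocol 5.9.10 (Missing Data) closes the statistical section with a rule on where excluded data are shown: "Data that are excluded from the descriptive or inferential analyses will be included in the subject data listings". It goes on: "This will include data from subjects not in the particular analysis population, measurements from unscheduled visits, or extra measurements", the last item referring to repeat analyses of one plasma sample. Nothing in that section separates safety data from PK/PD data.

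Unscheduled laboratory values are foreseeable. Below Table 5-2, Protocol 5.7.4.2 states: "The investigator or designee may repeat the clinical laboratory tests if deemed appropriate". No section says which result is then used in the summaries.

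The planned safety summaries are these:

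- **Laboratory.** Protocol 5.9.8.2 gives descriptive statistics including minimum and maximum, classifies results against reference ranges, and says that the number and "percentage of subjects with abnormal laboratory results will be provided". SAP 7.7.2 keeps the statistics and the classification but omits that count.
- **ECG.** SAP 7.7.4 says, as Protocol 5.9.8.4 does: "The incidence of pathological ECG interpretive statements at Baseline and during treatment will be assessed among the treatments". The Protocol also has numerical ECG summaries by arm and time point; SAP 7.7.4 does not.
- **Vital signs.** Protocol 5.9.8.3 states: "Vital sign measurements and changes from baseline will be summarized using descriptive statistics", by arm and time point. The Safety paragraph of the Protocol Synopsis adds: "All values will be evaluated for clinically notable results".

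SAP 6.1 deals with quantification limits, missing PK/PD data and the choice of baseline. The listing-only rule in SAP 7 concerns subjects outside an analysis population. Neither section mentions unscheduled measurements, and nor do SAP 7.7.2 to 7.7.4.

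**The concern.** Leaving unscheduled values out of means by time point is ordinary practice, because they belong to no nominal time. A subject-level summary is different. Whether a subject ever had an abnormal result, how extreme it was, and whether a pathological ECG statement occurred after dosing do not depend on the visit being planned. A test taken for cause is more likely than a routine one to show an abnormality, so dropping it from these outputs can remove the very information they exist to report.

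The stake is concrete. Protocol 5.1.3 names hepatic injury and decreased blood counts as risks of both drugs and refers to monitoring by liver tests and blood counts. The objective evidence for both is laboratory values. If a transaminase peak or a low count is found only on an unscheduled draw, the arm-level laboratory table would not show it.

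**Working it through.** The documents give no figure for this point, so the check compares texts and adds a simple scale calculation.

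**1. Does the rule reach safety data?** Section 5.9.10 follows 5.9.8 (Safety Analyses) and speaks of descriptive analyses. Descriptive analysis is how 5.9.8.2 to 5.9.8.4 handle laboratory, vital-sign and ECG data. The phrase about duplicate analyses of a plasma sample is a separate item joined by the word or, so it does not confine the unscheduled-visit item to PK. On its plain wording the rule reaches safety data.

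**2. Does any other section bring the values back?** Protocol 5.9.8.2 to 5.9.8.4 and SAP 6.1, 7 and 7.7.2 to 7.7.4 contain no such statement. The Synopsis sentence on vital signs says that all values are evaluated, but it assigns them to no table and is hard to square with 5.9.10.

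**3. Which outputs are affected?**

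| Output | Tied to a time point? | Effect of the exclusion |
|---|---|---|
| Vital-sign statistics (Protocol 5.9.8.3, SAP 7.7.3) | Yes | Ordinary practice |
| Numerical ECG statistics (Protocol 5.9.8.4 only) | Yes | Ordinary practice |
| Subjects with abnormal laboratory results (Protocol 5.9.8.2 only) | Not stated | Count can only fall or stay the same |
| Laboratory minimum and maximum (Protocol 5.9.8.2, SAP 7.7.2) | Not stated | Range can only narrow or stay the same |
| ECG-statement incidence (Protocol 5.9.8.4, SAP 7.7.4) | No: baseline and on treatment | Count can only fall or stay the same |

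The one-sided effect follows from how these outputs are built. A count of subjects with any abnormal value, or a minimum and maximum, taken over part of the data cannot exceed the same quantity taken over all of it. For the laboratory count this assumes one count per subject over the study, which the Protocol does not specify.

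**4. Scale.** There are 12 subjects per arm (Protocol Table 5-1). If k subjects in an arm have an abnormal value only at an unscheduled visit, the arm's rate falls by k/12:

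- k = 1: 1/12 = 8.3 percentage points.
- k = 2: 2/12 = 16.7 percentage points. If these are the only two abnormal subjects, the table shows 0/12 = 0% instead of 16.7%.
- If the subject's scheduled value was already abnormal, the count does not change, but a more extreme unscheduled value is lost from the minimum or maximum.

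No section gives a value for k. The spacing of scheduled safety tests is set in Table 9-1, which was not in the text available for this check, so k cannot be estimated.

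**5. Where could unscheduled values come from?** Besides repeat laboratory tests, Protocol 5.6.1.1 foresees longer stays for safety reasons. Protocol 5.7.4.1.2 requires related adverse events to be followed until they resolve or stabilize, and serious ones until resolution. SAP 3.1 has groups D to G leaving on Day 10 and returning on Day 14, whereas Protocol 5.1 keeps them in house to Day 14.

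**The case against.** A reader might infer that for-cause findings never reach any safety summary. The documents do not support that. Protocol 5.7.4.1.1 defines an adverse event to include abnormal laboratory findings and other untoward signs, whatever the visit. Section 5.7.4.1.2 requires all adverse events to be recorded until discharge or early termination. Treatment-emergent events are tabulated by arm (Protocol 5.9.8.1, SAP 7.7.1), and all data are listed. This safeguard is real but partial. Event tables hold coded events, not values, and they do not correct a count defined by reference ranges.

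A reader might also infer that every arm is biased towards normal, most of all the arms with most reactions. The documents give no frequency of unscheduled tests and no pattern by arm, and repeats are allowed simply when judged appropriate. A repeat after an abnormal scheduled result may be normal, and the subject's classification then stands.

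Three further objections have weight:

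- Section 5.9.10 sits under a missing-data heading and says where excluded data are shown. The exclusion is implied there and is not set out in the safety sections.
- It refers to unscheduled visits. Subjects are confined for most or all of the study, so an in-house repeat may not qualify. This narrows the rule's reach, but the term is undefined.
- The SAP does not repeat the rule, and its ECG incidence is not limited to scheduled recordings. A programmer could therefore include or omit the values.

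These objections reduce certainty about the effect. They do not remove the need to say which values count.

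**Conclusion.** The point holds in a limited form. On its plain wording, Protocol 5.9.10 keeps unscheduled-visit values out of the subject-level laboratory count, the laboratory extremes and the ECG-statement incidence, and the SAP gives no contrary instruction. The event itself can still reach the adverse-event tables; the measurement is confined to listings.

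The size is 8.3 percentage points per affected subject in an arm of 12. That is a scale and not a forecast. It assumes 12 evaluable subjects, a count made once per subject over the study, and a subject with no abnormal scheduled value.

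The matter is worth correcting before tables are programmed, but it is modest. Safety is not among the stated objectives or endpoints (Protocol 3 and 4), no testing of laboratory data is planned, and the neopterin analysis is untouched.

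**What to change.** 1. In Protocol 5.9.10, limit the exclusion of unscheduled measurements to by-time-point summaries and PK/PD parameters.
2. In Protocol 5.9.8.2 to 5.9.8.4 and SAP 7.7.2 to 7.7.4, state that subject-level abnormality counts, ECG-statement incidence and the worst post-dose value use all post-dose measurements, including unscheduled and repeat ones. Make clear that in-house repeats are covered.
3. Restore in SAP 7.7.2 the Protocol's count and percentage of subjects with abnormal laboratory results.
4. Report the scheduled-only count beside the all-measurements count. Subjects tested more often have more chances to show an abnormal value, and the second count lets a reader see how much that contributes.

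The cost is about a sentence in each affected section, one programming flag and an extra column or row in the tables. No study procedure or primary analysis changes.

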## **5.10. Data Quality Assurance**

Completed eCRFs are required for each subject randomly assigned to study drug. Electronic data entry will be accomplished through the ClinSpark® remote electronic data capture system, which allows for on-site data entry and data management. This system provides immediate, direct data transfer to the database, as well as immediate detection of discrepancies, enabling site coordinators to resolve and manage discrepancies in a timely

manner. Each person involved with the study will have an individual identification code and password that allows for record traceability. Thus, the system, and subsequently any investigative reviews, can identify coordinators, investigators, and individuals who have entered or modified records.

Furthermore, the investigator retains full responsibility for the accuracy and authenticity of all data entered into the electronic data capture system. The completed dataset and their associated files are the sole property of the sponsor and should not be made available in any form to third parties, except for appropriate governmental health or regulatory authorities, without written permission of the sponsor.

## **6. Ethical Considerations**

### **6.1. Ethical Conduct of the Study**

This study will be performed in accordance with the recommendations guiding physicians in biomedical research involving human subjects adopted by the 18th World Medical Association General Assembly, Helsinki, Finland, 1964 and later revisions, as well as, United States Title 45 Code of Federal Regulations (CFR) Part 46 GCP, and International Council for Harmonisation (ICH) guidelines describing technical requirements for registration of pharmaceuticals for human use.

### **6.2. Institutional Review Board (IRB)**

After the protocol is finalized and approved by FDA, FDA staff with primary responsibility for the FDA's involvement with the project (i.e., the FDA Project Lead) will submit the protocol and associated documentation to FDA's Office of the Chief Scientist to facilitate an Institutional Review Board Authorization Agreement (IAA) with FDA as the relying institution. The FDA Project Lead or investigator will provide the local IRB (i.e., Advarra) with all required documents, including the study protocol and informed consent form. The study will not be initiated until appropriate IRB approval is obtained from the local IRB. The investigator will provide the FDA Project Lead with copies of the approval documents for the protocol, informed consent form, and all recruiting materials. The sponsor will provide a copy of the local IRB approval letter to the investigator or designee before the study is initiated. The local IRB will also receive copies of any original or amended information sheets or pamphlets given to the study subject in support of the informed consent process and any advertisements or other recruitment material. Such materials will not be employed in the study before approval by the local IRB.

Subjects will be informed that they have the right to contact the local IRB or Office for Human Research Protections if they have any questions, concerns, complaints, or believe they have been harmed by the participation in this research study as a result of

investigator negligence. Subjects will be given the address and phone number of the local IRB.

## **7. Administrative Procedures**

### **7.1. Responsibilities of the Investigator**

The following administrative items are meant to guide the investigator in the conduct of the study but may be subject to change based on industry and government standard operating procedures, working practice documents, or guidelines. Changes may be reported to the IRB but will not result in protocol amendments.

#### **7.1.1 Form FDA 1572**

The investigator will complete and sign the Form FDA 1572.

#### **7.1.2 Adherence to Protocol**

The investigator agrees to conduct the study as outlined in this protocol in accordance with the ICH E6(R2) and all applicable guidelines and regulations.

#### **7.1.3 Reporting Requirements**

By participating in this study, the investigator agrees to submit reports of SAEs according to the time line and method outlined in the protocol (Section 5.7.4.1.2). In addition, the investigator agrees to submit reports to the IRB as appropriate. The investigator also agrees to provide the sponsor with an adequate report shortly after completion of the investigator's participation in the study.

#### **7.1.4 Source Documentation**

By participating in this study, the investigator agrees to maintain adequate case histories for the subjects treated as part of the research under this protocol. The investigator agrees to maintain accurate eCRFs and source documentation as part of the case histories.

#### **7.1.5 Retention of Records**

The investigator agrees to keep the records stipulated in this protocol and those documents that include (but are not limited to) the study-specific documents, identification log of all participating subjects, medical records, source worksheets, all original signed and dated informed consent forms, subject authorization forms regarding the use of personal health information (if separate from the informed consent form), copies of all eCRFs, query responses, and detailed records of drug disposition, to enable evaluations or audits from regulatory authorities, the sponsor, or its designees.

Furthermore, ICH 4.9.5 requires the investigator to retain essential documents specified in ICH E6(R2) (Section 8) until at least 2 years after the last approval of a marketing application for a specified drug indication being investigated or, if an application is not approved, until at least 2 years after the investigation is discontinued and regulatory authorities are notified. In addition, ICH 4.9.5 states that the study records should be retained until an amount of time specified by applicable regulatory requirements or for a time specified in the clinical study site agreement between the investigator and sponsor.

Refer to the clinical study site agreement for the sponsor's requirements on record retention. The investigator should contact and receive written approval from the sponsor before disposing of any such documents.

### **7.1.6 Financial Disclosure and Obligations**

The investigator is required to provide financial disclosure information to allow the sponsor to submit the complete and accurate certification or disclosure statements required under 45 CFR 46. In addition, the investigator must provide to the sponsor a commitment to update this information promptly if any relevant changes occur during the course of the investigation and for 1 year after the completion of the study.

Neither the sponsor nor the study clinic is financially responsible for further testing or treatment of any medical condition that may be detected during the screening process.

